#### Idelalisib treatment

- Change in idelalisib dose (date), including interruption of dosing and reason
- Co-medications (changes)

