## 9.7. Data Analysis

Categorical variables will be summarized descriptively by number and percentage of patients in each categorical definition including 95% confidence intervals. Continuous variables will be summarized descriptively by mean, standard deviation, median, lower quartile, upper quartile, minimum and maximum.

Multivariate Poisson regression analyses will be used to estimate rates of ADRs and SADR, adjusted for potential confounders (demographics, baseline disease assessment, medical history, treatment history, treatment changes; see section 9.3).

Multivariate Cox Proportional Hazard analyses will be used to model time-to-event data, and time to ADRs, SADR and AESIs.

Kaplan Meier curves will be used to illustrate time-to-event analyses.

Special focus will be given to the differences in retrospective and prospective data collection. Although not by intention, data might be collected differently in retrospect compared to patient's data that will be collected prospectively. Retrospective patients will be recruited through systematic search of the sites' patient data management system, whereas prospective data will be collected from those patients prescribed idelalisib after the start of the study. Behavioral changes of the site staff after the initiation of the study might play a role in differential data collection. Thus, missing data for the retrospective data might be an issue. Stratified analyses will be conducted to account for this potential bias.

The extent of missing data in the study will be described and tabulated. Imputation methods will be used to account for missing values in the dataset for those variables used in multivariate modeling (demographics, baseline disease assessment, medical history, treatment history) and changes in idelalisib treatment following the current ENCePP guidelines (Methodological Standards in Pharmacoepidemiology: Section 5.3. Handling of missing data;

[http://www.encepp.eu/standards\\_and\\_guidances/methodologicalGuide5\\_3.shtml](http://www.encepp.eu/standards_and_guidances/methodologicalGuide5_3.shtml) {Rubin 1987}, {Moons 2006}, {Welch 2014}. Multiple imputation by chained equations (MICE) as sequential regression multiple imputation will be used handling of missing data {Azur 2011}. Using MICE, missing values are imputed based on the observed values for a given individual and the relationships within the data for other participants.

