## 9.9. Limitations of the Research Methods

This study has the characteristic disadvantages of retrospective studies, for example selection bias, information bias and missing values.

In order to reduce selection bias, subject's eligibility criteria have been well defined. However, this is not a type of bias easy to prevent or measure. A selection bias introduced by the choice of sites that contribute patient data cannot totally be avoided. However, a selection of sites in multiple countries will help to reduce this kind of bias. Countries selected for this study include

those in which an EAP for idelalisib in refractory FL patients has been running since the time of MA for idelalisib. Additional countries without an active EAP were included based on the volume of idelalisib prescribing since the time of the MA. Sites within these countries will be selected based on whether they have been prescribing idelalisib for refractory FL patients in accordance with the approved product information for idelalisib. Thus, the final number of sites per country will depend on the available number of patients per site.

This study is a non-comparative non-interventional study, as a result confounding by indication (ie confounding indicated by study drug) should be a minimal issue in the absence of a comparator. Multivariate analyses will aim to minimize potential confounding by indication by including disease assessment and according treatment in the analyses.

In reference to protocol Section 10.3 (Informed Consent) Gilead will collect informed consents for patients being identified prospectively. Informed consent will not be collected for deceased patients or patients identified retrospectively, unless specifically required by an appropriate ethics committee or required by country National Data Protection Laws for a participating centre. Not using an informed consent form (ICF) for deceased patients or patients identified in retrospect allows incorporating data which otherwise would lead to a patient population that is strongly biased towards survivors and a potential risk of death could be underestimated.

Information bias can be prevented by using standard measurement instruments, like eCRF and appropriate training of personnel entering the data. Appropriate training of personnel entering data is also important to avoid missing values when checking the patients' medical records.

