## **11. MANAGEMENT AND REPORTING OF SAFETY INFORMATION**

### **11.1. Investigator Reporting Requirements to Gilead**

The following safety information is required to be collected and reported for this study from the time the subject is prescribed idelalisib until 6 months after completion of therapy or early discontinuation of idelalisib.

- Adverse Events (AEs) leading to dose modification, interruption or discontinuation
- All Serious Adverse Events (SAEs)
- Special Situation Reports (SSRs)
- Adverse Drug Reactions (ADRs)
- Serious Adverse Drug Reactions (SADRs)
- Pregnancy or partner-pregnancy

Timelines for reporting to Gilead are as follows:

- Within 3 calendar days of knowledge of all SAEs
- Within 30 calendar days of knowledge of any non-serious AEs, SSRs, Pregnancy or partner-pregnancy

Details of the methods for reporting AEs, ADRs, SAEs, SADRs or SSRs to Gilead DSPH will be described in the CRF completion guidelines. If reporting of events is by electronic submission via eCRF, this method must always be used unless the eCRF system is not functioning. If for any reason it is not possible to record death, AE, ADRs, SAE, SADRs and SSR information electronically, the details should be recorded on the appropriate paper reporting forms (e.g., the Non-Interventional Study AE/SAE Report Form or the Non-Interventional Study Special Situations Report Form) and submitted by fax or e-mail, within the timelines given above to Gilead DSPH:

E-mail:           Safety\[contact]

[contact]

As soon as it is possible to do so, any death, AE, ADR, SAE, SADR and SSR reported via paper must be transcribed into the eCRF database according to the instructions in the eCRF completion guidelines.

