### 11.3. Definitions

#### 11.3.1. Adverse Events

An **adverse event** (AE) is any untoward medical occurrence in a clinical study subject administered a pharmaceutical product, which does not necessarily have a causal relationship with the treatment. An AE can therefore be any unfavourable and/or unintended sign, symptom, or disease temporally associated with the use of a medicinal product, whether or not considered related to the medicinal product. AEs may also include lack of efficacy, overdose, drug abuse/misuse reports, or occupational exposure. Pre-existing events that increase in severity or change in nature during or as a consequence of participation in the clinical study will also be considered AEs.

This study will only collect AEs that lead to dose modification, interruption or discontinuation.

An AE does not include the following:

- Medical or surgical procedures such as surgery, endoscopy, tooth extraction, and transfusion. The condition that led to the procedure may be an AE and should be reported.
- Situations where an untoward medical occurrence has not occurred (e.g., hospitalization for elective surgery, social and/or convenience admissions)
- Any medical condition or clinically significant laboratory abnormality with an onset date before the consent form is signed. These are considered to be pre-existing conditions and should be documented on the medical history CRF (if applicable).

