#### **11.4. Clinical Laboratory Abnormalities**

Laboratory abnormalities without clinical significance are not recorded as safety events. However, laboratory abnormalities (e.g., clinical chemistry, hematology, and urinalysis) that require medical or surgical intervention or lead to drug interruption, modification, or discontinuation and considered to be causally associated with the medicinal product must be recorded as an AE, or an SAE, if applicable. In addition, laboratory or other abnormal assessments (e.g., electrocardiogram, x-rays, vital signs) that are associated with signs and/or symptoms must be recorded as an AE or SAE if they meet the definition of an AE or SAE as described in Section 11.3. If the laboratory abnormality is part of a syndrome, record the syndrome or diagnosis (e.g., anemia), not the laboratory result (i.e., decreased hemoglobin).

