3.1 Is the study design described? (e.g. cohort, case-control, cross-sectional, new or alternative design)				9.1
3.2 Does the protocol specify whether the study is based on primary, secondary or combined data collection?				9.3
3.3 Does the protocol specify measures of occurrence? (e.g. incidence rate, absolute risk)				9.7
3.4 Does the protocol specify measure(s) of association? (e.g. relative risk, odds ratio, excess risk, incidence rate ratio, hazard ratio, number needed to harm (NNH) per year)				-
3.5 Does the protocol describe the approach for the collection and reporting of adverse events/adverse reactions? (e.g. adverse events that will not be collected in case of primary data collection)				9, 11

Comments:

Only incidence rates (crude and adjusted) will be calculated. No comparisons will be made

Section 4: Source and study populations	Yes	No	N/A	Section Number
4.1 Is the source population described?				9.2
4.2 Is the planned study population defined in terms of:				
4.2.1 Study time period?				6
4.2.2 Age and sex?				-
4.2.3 Country of origin?				9.2
4.2.4 Disease/indication?				9.2
4.2.5 Duration of follow-up?				9.1
4.3 Does the protocol define how the study population will be sampled from the source population? (e.g. event or inclusion/exclusion criteria)				9.2

Comments:

Results will distinguish for age and sex. But the population will not be specifically defined for both characteristics.

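### The Poisson model for ADR and SADR rates adjusts for post-baseline treatment changes, which the counted events can themselves cause

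*Protocol*

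**What the plan says.** Section 9.7 names the model and its outcomes: "Multivariate Poisson regression analyses will be used to estimate rates of ADRs and SADR". The same sentence then gives the covariates, since the estimates are to be "adjusted for potential confounders (demographics, baseline disease assessment, medical history, treatment history, treatment changes; see section 9.3". The first four covariate groups are listed in section 9.3 under treatment initiation. The fifth is not. Under the observation period, section 9.3 lists "Change in idelalisib dose (date), including interruption of dosing and reason".

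Three places in section 11 link recorded events to such changes:

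- Section 11.1 lists as reportable "Adverse Events (AEs) leading to dose modification, interruption or discontinuation". SAEs, ADRs and SADRs have their own lines, without that condition.
- Section 11.3.1 says: "This study will only collect AEs that lead to dose modification, interruption or discontinuation".
- Section 11.4 covers laboratory abnormalities. One route to being recorded applies to those that "lead to drug interruption, modification, or discontinuation and considered to be causally associated with the medicinal product must be recorded as an AE"; need for medical or surgical intervention is another.

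On the purpose of adjustment, section 9.9 says that confounding by indication "should be a minimal issue in the absence of a comparator". The Annex 1 checklist comments on study design: "Only incidence rates (crude and adjusted) will be calculated. No comparisons will be made".

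**The concern.** A confounder precedes the outcome and distorts a comparison between exposure groups. Treatment changes meet neither condition here. They arise after baseline, often because an adverse reaction has occurred, and there is no second group to compare. For a causally associated laboratory abnormality, the dose change may even be the reason that the event was recorded.

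A model that conditions on such a variable moves part of the event count into the covariate's coefficient. The rate reported for a given covariate value then depends on how often clinicians change treatment after an event. The study was required in order to describe safety in refractory FL, so a rate that is too low for this reason would mislead on its main output. The protocol chooses this covariate explicitly, so the point is not a detail left to the SAP.

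**Working it through.** **The plan's own figure.** The protocol gives no adjusted rate to reproduce. Its one related figure is the study size in section 9.5. With n = 1.96² × p(1 − p)/d², the three columns give 297.5 (3.2%, 0.02), 303.0 (5.2%, 0.025) and 299.7 (7.6%, 0.03), in line with 300. This point does not affect that figure.

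**Inputs from the protocol.** Median treatment period 8 months (9.5); follow-up to 6 months after discontinuation (9.1); longest window 3 + 2.5 = 5.5 years (9.5).

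**Assumed inputs, varied over a range.** True event rate λ = 0.1, 0.3 or 0.6 per patient-year; share q of events that trigger a treatment change = 0, 0.3, 0.5, 0.8 or 1; unrelated changes at b = 0.1 or 0.3 per patient-year; covariate coded ever/never.

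**Algebra.** Split the events into those that trigger a change (rate qλ) and those that do not (rate (1 − q)λ). A patient with no change has, by definition, none of the first kind. The rate in that group is therefore (1 − q)λ. For λ = 0.30 this is 0.7 × 0.30 = 0.21, 0.5 × 0.30 = 0.15 and 0.2 × 0.30 = 0.06.

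**Simulation.** Follow-up was exponential treatment time with median 8 months, plus 6 months, capped at 5.5 years. A Poisson regression with a log person-time offset was fitted with and without the ever-changed covariate, on 20,000 patients and three repeats per scenario. Results for λ = 0.30, with ranges over the two values of b:

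| q | No change | At covariate mean | Change | Standardised |
|---|---|---|---|---|
| 0 | 0.30 | 0.30 | 0.30 | 0.30 |
| 0.3 | 0.204–0.208 | 0.256–0.266 | 0.392–0.510 | 0.30 |
| 0.5 | 0.151–0.154 | 0.223–0.237 | 0.420–0.549 | 0.30 |
| 0.8 | 0.059–0.061 | 0.136–0.166 | 0.456–0.577 | 0.30 |
| 1 | 0 | not estimable | 0.466–0.582 | 0.30 |

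One row by hand (q = 0.5, b = 0.1): the no-change rate is 0.154, the fitted rate ratio for change is 3.568, and 29.1% of patients have a change. At change: 0.154 × 3.568 = 0.549. At the mean: 0.154 × 3.568^0.291 = 0.223.

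The standardised column equals the crude rate by construction. A Poisson model with an intercept and log link makes fitted events sum to observed events.

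**With baseline covariates only**, the adjusted rate recovers 0.10, 0.30 and 0.60 to within about 0.005 in every scenario.

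**With person-time split at the change date** (λ = 0.30, q = 0.5, b = 0.2), the rate before a change is 0.30, which is correct. After a change it is 0.30, 0.15 or 0.60 if the change multiplies later risk by 1, 0.5 or 2. The overall rates are then 0.30, 0.26 and 0.38. The period rates are valid for their periods, but they are not the overall rate.

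**The case against.** A reader might infer that the adjusted rates must be biased low and cannot be interpreted. The document does not support that. Section 9.7 does not say whether the covariate is ever/never or time-dependent, or at which covariate values the rate is reported. The table shows bias in both directions, and none after standardisation. Dates of dose changes are collected, so a correctly ordered time-dependent coding is feasible, and it would not have this reverse-causation bias. The SAP may specify it. This stands, and it limits what can be said about direction.

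A second objection is that the modelled outcomes are ADRs and SADRs, which section 11.1 collects whether or not treatment changed. This also stands: it is not established that these events enter the data only through a dose change. The literal rule in section 11.3.1 would correspond to q = 1 for non-serious events, but it differs in scope from section 11.1, and the two need reconciling. The objection does not remove the problem. A reaction collected unconditionally can still lead to a dose change, and any q above 0 is enough.

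Third, crude rates are planned and no hypothesis is tested. That limits the damage to the adjusted figures but does not justify the covariate.

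A reader might also infer that the model has too many parameters for the event counts implied by section 9.5. Those proportions are for single grade 3 outcomes, the Poisson model is for ADRs and SADRs, and the study size is stated in patient-years. That inference is not made here.

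**Conclusion.** The concern holds in a limited form. Section 9.7 wrongly names as a confounder a post-baseline variable that the counted events can cause, in a study with no contrast to confound.

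Under ever/never coding, the rate at no change is too low by the fraction q: 30%, 50% or 80% for the three shares shown. At λ = 0.30 the rate at the covariate mean is about 11–15%, 21–26% or 45–55% too low for the same shares. The rate at change is about 31–92% too high across them. Standardised rates are not biased, and neither are crude rates.

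These sizes rest on assumed values of λ, q and b and on ever/never coding, none of which the protocol gives. The mechanism needs only that some counted events lead to a treatment change.

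**What to change.** In section 9.7, delete treatment changes from the covariate list of the Poisson model, so that adjustment uses baseline covariates only, and carry the same wording into the SAP.

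If the effect of dose changes is of interest, describe it as a separate analysis: split each patient's person-time at the change date, count only changes that precede the event, and report rates before and after. Do not present these as the overall adjusted rate.

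The cost is one phrase in the protocol, matching SAP wording and, if wanted, one extra table. No further data are needed, because section 9.3 already collects the date of and reason for each change. The crude rates and the imputation plan need no change on this account.

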**Study Size:**

This study aims to include patients who have been or are currently being treated with idelalisib according to the product information and treatment guidelines in routine clinical practice for the treatment of refractory FL, after marketing authorisation in the EU (September 2014) and Australia (January 2015).

Assuming a median treatment period of 8 months, a retrospective timeframe of around 3 years and a prospective observation period of 2.5 years, it is expected that data of approximately 300 patient-years will be collected.

Patients will be identified and enrolled in Europe (pending outcome of study feasibility: Australia, Austria, Belgium, France, Germany, Greece, Ireland, Italy, Portugal, Spain, Sweden, Switzerland and the United Kingdom) and Australia.

---

**Data Analysis:** Continuous variables will be summarized by mean, standard deviation, median, lower quartile, upper quartile, minimum and maximum. Categorical variables will be summarized by number and percentage of patients in each categorical definition including 95% confidence intervals.

Multivariate Poisson regression analyses will be used to estimate adjusted rates of ADRs and SADR.

Multivariate Cox Proportional Hazard analyses will be used to model time-to-event data, and time to ADRs and SADR.

Kaplan Meier will be used to illustrate time-to-event analyses.

Stratified analyses will be used to account for potential behavioral changes of the site staff after the initiation of the study that might introduce bias between retrospective and prospective data collection.

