## **9. RESEARCH METHODS**

### **9.1. Study Design**

A retrospective cohort study enrolling patients who were or are being treated with idelalisib for refractory FL according to the product information and treatment guidelines in routine clinical practice after the country specific approval date.

Patient's data will be collected from the date of treatment initiation with idelalisib until 6 months after treatment discontinuation.

The study design allows for both retrospective and prospective data to be collected. The start of data collection is defined as the entry of the first patient into the eCRF. In the data analysis, any data prior to the start of the study will be considered retrospective. Any data after that date will be considered prospective.

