### **9.5. Study Size**

This study aims to include patients who have been or are currently being treated with idelalisib according to the product information and treatment guidelines for the treatment of refractory FL after marketing authorization in the EU (September 2014) and Australia (January 2015).

Prevalence data for iNHL in the EU are limited. HAEMACARE, a European cancer registry-based project on hematologic malignancies funded by the European Commission, provides European incidence rates but not prevalence data {Sant 2010}. Australian prevalence data could not be identified. The Decision Resources Group (<http://www.decisionresourcesgateway.com/index.aspx>) estimated a 10-year limited-duration prevalence for FL in 5 major EU countries (France, Germany, Italy, Spain, and United Kingdom) over the 2011-2021 forecast period based on cancer registry databases in the EU-5. The EU prevalence estimates for FL ranged from 1.4 (Spain) in 2011 to 3.1 (France) per 10,000 in 2015 (RMP, section 1.1.1.4.2).

Based on the pivotal studies 101-09, GS-US-313-0124 and GS-US-313-0125 the median treatment period is estimated to be 8 months, taking into account that studies GS-US-313-0124 and GS-US-313-0125 were terminated early. Thus, a retrospective timeframe of around 3 years and a prospective observation period of another 2.5 years allow data of approximately 300 patient-years to be collected.

A sample size of 300 patient-years is based on the chance to find a proportion of adverse events of 3.2% with a precision of 2%. The table below shows the relationship between various detectable single proportions of AEs and precision of the estimate.

Proportions found in studies 101-09, GS-US-313-0124 and GS-US-313-0125 were 1.4% ( Grade 3 diarrhea and/or colitis), 2.0% (( Grade 3 febrile neutropenia), 6.1% (( Grade 3 infection) and 8.1% (( Grade 3 rash).

Proportion of AEs	3.2%	5.2%	7.6%
Precision	0.02	0.025	0.03

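### Section 9.7 commits to multivariable Cox models for undefined AESIs with no condition on event counts, and the four outcome proportions the protocol gives are too low for such models if AESIs are analysed individually

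*Protocol*

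**What the plan says.** Section 9.7 of the protocol commits to a method: "Multivariate Cox Proportional Hazard analyses will be used to model time-to-event data, and time to ADRs, SADR and AESIs". The Data Analysis entry of the synopsis (section 4) has the same sentence without AESIs: "Multivariate Cox Proportional Hazard analyses will be used to model time-to-event data, and time to ADRs and SADR". AESI is not defined; sections 8 and 9.3 speak of HOIs and list them.

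The Cox sentence names no covariates. Section 9.7 attaches its explicit confounder list to the Poisson models for ADRs and SADRs. Its missing-data paragraph then plans imputation for "those variables used in multivariate modeling (demographics, baseline disease assessment, medical history, treatment history"), together with changes in idelalisib treatment. Section 9.9 adds: "Multivariate analyses will aim to minimize potential confounding by indication by including disease assessment and according treatment in the analyses".

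Section 9.5 sizes the study on the precision of one proportion: "A sample size of 300 patient-years is based on the chance to find a proportion of adverse events of 3.2% with a precision of 2" per cent. It gives expected proportions for four outcomes: "Proportions found in studies 101-09, GS-US-313-0124 and GS-US-313-0125 were 1.4" per cent for grade 3 diarrhoea and/or colitis, then 2.0% for febrile neutropenia, 6.1% for infection and 8.1% for rash, all grade 3.

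Section 3 of the ENCePP checklist (Annex 1) marks measures of association as not applicable. Its comment limits the output to crude and adjusted incidence rates and rules out comparisons.

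**The concern.** A Cox model draws its information from the number of patients with an event, not from the number of patients. Section 9.7 applies a multivariable model to AESIs without condition, while section 9.5 implies that some of these outcomes will occur in only a handful of patients. With so few events, a covariate level often contains none or all of them. The maximum likelihood estimate is then infinite, or it is finite but very imprecise.

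The regulator asked for this study in order to describe safety in an uncontrolled indication. An unstable covariate hazard ratio for a serious toxicity could be taken for a risk factor. Such hazard ratios are also measures of association, which the checklist says the study does not produce.

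**Working it through.** **1. The protocol's own size.** For a single proportion with a 95% Wald interval, n = 1.96² × p(1 − p) / d².
- p = 3.2%, d = 0.02: n = 297.5
- p = 5.2%, d = 0.025: n = 303.0
- p = 7.6%, d = 0.03: n = 299.7

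The stated 300 is reproduced, but as 300 persons. The protocol labels it patient-years and gives no patient number.

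**2. Range for the number of patients (assumption).** Section 9.5 says "the median treatment period is estimated to be 8 months", and section 9.1 says "Patient's data will be collected from the date of treatment initiation with idelalisib until 6 months after treatment discontinuation".
- Counting only 8 months each: 300 / (8/12) = 450 patients.
- Exponential treatment time with median 8 months has mean 8 / ln 2 = 11.54 months. Adding 6 months gives 17.54, and 300 / (17.54/12) = 205 patients.

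**3. Number of parameters (assumption).** From section 9.3: age, sex, organ involvement, bulky nodes, marrow involvement, time since diagnosis, ECOG and number of prior regimens (8 parameters), FL 1/2/3a (2) and Ann Arbor stage (3) make 13. One further category makes 14. One parameter for each of the ten variables makes 10, and dropping one or two (ECOG is recorded only where available) leaves 9 or 8. Treatment changes after baseline are not counted.

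**4. Expected events = N × p, and events per parameter at N = 300.**

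| Outcome | p | N = 205 | N = 300 (95% binomial range) | N = 450 | Per parameter: 14 / 13 / 8 |
|---|---|---|---|---|---|
| Diarrhoea/colitis | 1.4% | 2.9 | 4.2 (1–9) | 6.3 | 0.30 / 0.32 / 0.53 |
| Febrile neutropenia | 2.0% | 4.1 | 6.0 (2–11) | 9.0 | 0.43 / 0.46 / 0.75 |
| Infection | 6.1% | 12.5 | 18.3 (11–27) | 27.5 | 1.31 / 1.41 / 2.29 |
| Rash | 8.1% | 16.6 | 24.3 (15–34) | 36.5 | 1.74 / 1.87 / 3.04 |

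The most favourable corner, 450 patients and 8 parameters, gives 36.5 / 8 = 4.6 for rash and 6.3 / 8 = 0.8 for diarrhoea/colitis.

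**5. Behaviour of the fit.** Unpenalised Cox models were fitted to simulated cohorts of 300 with all covariate effects zero and assumed covariate prevalences. There were 300 datasets per scenario for 14 and 9 parameters, and 250 for 13. No finite fit means no event, non-convergence or an absolute log hazard ratio of 8 or more. An extreme hazard ratio is one above 3 or below 1/3 for at least one covariate.

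| Outcome | No finite fit: 14 / 13 / 9 | Extreme hazard ratio among finite fits: 14 / 13 / 9 |
|---|---|---|
| Diarrhoea/colitis | 96% / 98% / 75% | 100% / (5 fits only) / 74% |
| Febrile neutropenia | 91% / 90% / 56% | 93% / 79% (24 fits) / 69% |
| Infection | 25% / 35% / 3% | 68% / 67% / 33% |
| Rash | 17% / 20% / 1% | 54% / 54% / 15% |

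The 13-parameter runs used a shortened follow-up with mean 0.5 × 1 + 0.5 × 0.8 = 0.9 of the full period. Their event counts are therefore about 10% low, which is one reason they fail more often than the 14-parameter runs for infection and rash.

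**6. One covariate only.** For one balanced binary covariate the standard error of the log hazard ratio is √(4/events). The 95% interval then spans a factor exp(1.96 × √(4/events)) on either side: 6.8, 5.0, 2.5 and 2.2 for the four outcomes. Power to detect a hazard ratio of 2 is 11%, 13%, 32% and 40%.

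**The case against.** The strongest reply is that the conflict depends on how the text is read. Section 9.7 does not say each AESI, so a composite is not excluded. The Cox covariates are not listed, and naming variable groups for imputation does not put every item into every model. The final covariate set and the handling of sparse events are commonly settled in a statistical analysis plan, which is not shown here. Section 9.3 can also be read as placing febrile neutropenia inside one grouped infection outcome, which would remove the six-event case.

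Much of this stands. The parameter count is an assumption, and failure rates fall clearly from 14 parameters to 9. Only four outcomes have proportions: PML, SJS-TEN and bowel perforation may be rarer, while transaminase elevation, neutropenia and pneumonitis may be commoner. It does not clear the text, however. Section 9.7 fixes a method without condition for an undefined set of outcomes, and diarrhoea/colitis at about four events remains under any grouping of infections.

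Three stronger inferences are not supported:
- **That all these models fail.** With 9 parameters, infection and rash gave a finite fit in 97% and 99% of datasets.
- **That adjusted estimates would displace crude rates.** The checklist keeps both, and section 9.7 also plans percentages with 95% intervals. The adjusted Poisson rates are for ADRs and SADRs.
- **That false positives are inflated.** With 13 parameters, at least one p below 0.05 appeared in 34% (infection) and 39% (rash) of fitted runs. Thirteen independent 5% tests would give 1 − 0.95¹³ = 49%. The weakness is instability and imprecision, and the study tests no hypothesis.

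**Conclusion.** The concern holds in a limited form. If AESIs are the individual HOIs, the protocol's own proportions give about 4 to 24 events at 300 patients (about 3 to 36 across 205 to 450 patients) for the four outcomes that have a figure. At 300 patients and an assumed 8 to 14 parameters, that is about 0.3 to 3 events per parameter. Multivariable Cox models for the two rarest would mostly have no finite fit (56% to 98% of simulated datasets with 9 to 14 parameters). Those for infection and rash would usually fit but be unstable.

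This rests on the trial proportions carrying over to routine practice, on the assumed parameter count and covariate prevalences, and on reading AESI as individual HOIs. A reader might extend it to every HOI, to pooled ADRs and SADRs or to the Poisson models. The protocol gives no expected counts for the remaining HOIs or for the pooled outcomes, so no problem is shown there. The planned descriptive results are not threatened.

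**What to change.** In section 9.7 and the synopsis:

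- Define AESI, as the individual HOIs or as a named composite, and make the two Cox sentences agree.
- Make the crude incidence rate with an exact Poisson 95% confidence interval the reported estimate for each individual HOI.
- Make multivariable Cox modelling of an AESI conditional on a pre-stated minimum number of events per model parameter, using a short prespecified covariate set or Firth-penalised likelihood, and fit no regression when events are very few. As an illustration only, since the protocol sets no threshold: at 300 patients, 10 events per parameter would allow 0.4, 0.6, 1.8 and 2.4 parameters for the four outcomes, and 5 would allow 0.8, 1.2, 3.7 and 4.9.
- Reconcile any hazard ratio output with the Annex 1 checklist, either by amending its entry on measures of association and comparisons or by stating that covariate hazard ratios are descriptive.

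This needs no extra patients or data. The small cost is that adjusted results are not reported for rare HOIs, where they would not be reliable.
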